9.4.5 BASELINE DESCRIPTIVE STATISTICS

The following baseline variables and demographics will be compared for the two randomization groups: age, gender, race, ethnicity, baseline HbA1c, and BMI category.

9.4.6 PLANNED INTERIM ANALYSES

An unblinded interim futility analysis may be conducted after 12 participants have completed the study. Futility is defined as a participant incidence of >5 SAEs, a failure rate of $\geq 90\%$ on Day 5 for the investigational infusion set, or a forecasted probability of primary endpoint success at the end of the trial that is too low to justify continuing.

9.4.7 SUB-GROUP ANALYSES

N/A

9.4.8 TABULATION OF INDIVIDUAL PARTICIPANT DATA

Listings of the primary and secondary endpoints will be presented by patient and by time point for each treatment

9.4.9 EXPLORATORY ANALYSES

Exploratory analyses will use the both ITT and PP populations for analysis. All pharmacokinetic parameters (AUCs, t_{50} , C_{max} , t_{max} , MRT for the insulin concentration by time curve, etc.) will be estimated using non-compartmental models and log-transformed before analysis. Means for the two treatment groups will be compared in a mixed-effects (repeated-measures) linear model with treatment, day and period as fixed effects and participant as a random effect. The mean difference between treatments (on the log-scale) will be compared with a two-sided test using significance level 0.05. Then mean ratio and its 95% confidence interval will be calculated by inverse-transforming the mean difference and its 95% confidence interval. Trends over time within treatments will be compared with two-sided tests using significance level $\alpha=0.05$.

Kaplan-Meier device survival curves will be constructed for each device and then compared with a Cox regression analysis with a frailty term that accounts for the repeated-measures on participants.

10 SUPPORTING DOCUMENTATION AND OPERATIONAL CONSIDERATIONS

10.1 REGULATORY, ETHICAL, AND STUDY OVERSIGHT CONSIDERATIONS

10.1.1 INFORMED CONSENT PROCESS

In obtaining and documenting informed consent, the investigator must comply with applicable regulatory requirements (e.g., 45 CFR Part 46, 21 CFR Part 50, 21 CFR Part 56) and should adhere to ICH GCP. Prior to the beginning of the trial, the investigator should have the IRB's written approval for the protocol and the written informed consent form(s) and any other written information to be provided to the participants.

10.1.1.1 CONSENT AND OTHER INFORMATIONAL DOCUMENTS PROVIDED TO PARTICIPANTS

The consent form contains all required regulatory elements.

10.1.1.2 CONSENT PROCEDURES AND DOCUMENTATION

Informed consent is a process that is initiated prior to the individual's agreeing to participate in the study and continues throughout the individual's study participation. Consent forms will be Institutional Review Board (IRB)-approved and the participant will be asked to read and review the document. The investigator will explain the research study to the participant and answer any questions that may arise. A verbal explanation will be provided in terms suited to the participant's comprehension of the purposes, procedures, and potential risks of the study and of their rights as research participants. Participants will have the opportunity to carefully review the written consent form and ask questions prior to signing. The participants should have the opportunity to discuss the study with their family or surrogates or think about it prior to agreeing to participate. The participant will sign the informed consent document prior to any procedures being done specifically for the study. Participants must be informed that participation is voluntary and that they may withdraw from the study at any time, without prejudice. A copy of the informed consent document will be given to the participants for their records. The informed consent process will be conducted and documented in the source document (including the date), and the form signed, before the participant undergoes any study-specific procedures. The rights and welfare of the participants will be protected by emphasizing to them that the quality of their medical care will not be adversely affected if they decline to participate in this study.

10.1.1.3 STUDY DISCONTINUATION AND CLOSURE

This study may be temporarily suspended or prematurely terminated if there is sufficient reasonable cause. Written notification, documenting the reason for study suspension or termination, will be provided by the Sponsor to study participants, investigator, and sponsor. If the study is prematurely terminated or suspended, the Principal Investigator (PI) will promptly inform study participants, the Institutional Review Board (IRB), and will provide the reason(s) for the termination or suspension. Study participants will be contacted, as applicable, and be informed of changes to study visit schedule.

Circumstances that may warrant termination or suspension include, but are not limited to:

- Determination of unexpected, significant, or unacceptable risk to participants
- Demonstration of efficacy that would warrant stopping
- Insufficient compliance to protocol requirements
- Data that are not sufficiently complete and/or evaluable
- Determination that the primary endpoint has been met
- Determination of futility
- Three or more participants develop DKA
- Three or more participants develop severe hypoglycemia

Study may resume once concerns about safety, protocol compliance, and data quality are addressed, and satisfy the sponsor, and IRB.

10.1.2 CONFIDENTIALITY AND PRIVACY

Participant confidentiality and privacy is strictly held in trust by the participating investigators, their staff, and the sponsor(s) and their interventions. This confidentiality is extended to cover testing of biological samples and genetic tests in addition to the clinical information relating to participants. Therefore, the study protocol, documentation, data, and all other information generated will be held in strict confidence. No information concerning the study or the data will be released to any unauthorized third party without prior written approval of the sponsor.

All research activities will be conducted in as private a setting as possible.

The study monitor, other authorized representatives of the sponsor, representatives of the Institutional Review Board (IRB), regulatory agencies or pharmaceutical company supplying study product may inspect all documents and records required to be maintained by the investigator, including but not limited to, medical records (office, clinic, or hospital) and pharmacy records for the participants in this study. The clinical study site will permit access to such records.

The study participant's contact information will be securely stored at each clinical site for internal use during the study. At the end of the study, all records will continue to be kept in a secure location for as long a period as dictated by the reviewing IRB, Institutional policies, or sponsor requirements.

Study participant research data, which is for purposes of statistical analysis and scientific reporting, will be transmitted to and stored at the Sponsor. This will not include the participant's contact or identifying information. Rather, individual participants and their research data will be identified by a unique study identification number. The study data entry and study management systems used by clinical sites and by Sponsor research staff will be secured and password protected. At the end of the study, all study databases will be de-identified and archived at the Sponsor.

10.1.3 FUTURE USE OF STORED SPECIMENS AND DATA

Data collected for this study will be analyzed and stored at the Sponsor. After the study is completed, the de-identified, archived data will be transmitted to and stored at the Sponsor, for use by other researchers including those outside of the study. Permission to transmit data to the Sponsor will be included in the informed consent.

During the conduct of the study, an individual participant can choose to withdraw consent to have biological specimens stored for future research. However, withdrawal of consent with regard to biosample storage may not be possible after the study is completed.

When the study is completed, access to study data and/or samples will be provided through the Sponsor.

10.1.5 SAFETY OVERSIGHT

Serious Adverse Events will be reviewed within 24 hours of notification. Preliminary assessment will be conducted by the principal investigator or qualified designee. The sponsor Medical Monitor will be responsible for review all SAEs within 24 hours of notification. Non-serious adverse events will be reviewed per monitoring plan and at least monthly by sponsor Medical Monitor. Sponsor Medical Monitor will be a licensed clinician, e.g., MD, DO, PA, or RN. SAEs will be assessed by an MD or DO.

Upon review of the report, an adjudication will be issued: no action may be taken, the consent form may be revised, study procedures may be modified, or approval of the study may be suspended, pending further inquiry.

The qualifications of the Medical Monitor must be provided to NIDDK for approval.

10.1.6 CLINICAL MONITORING

Clinical site monitoring is conducted to ensure that the rights and well-being of trial participants are protected, that the reported trial data are accurate, complete, and verifiable, and that the conduct of the trial is in compliance with the currently approved protocol/amendment(s), with International Conference on Harmonization Good Clinical Practice (ICH GCP), and with applicable regulatory requirement(s).

Monitors will be appointed by Capillary Biomedical. Monitors will be trained with scientific and/or clinical knowledge and his/her qualifications will be documented. The Monitor will be familiar with the investigational product, protocol, consent form and any other written information given to the participant, sponsor's SOPs, and GCP and the relevant regulatory requirements.

Monitoring will be conducted with a combination of remote monitoring and on-site from time to time based on enrollment rate, occurrence of adverse events, etc. to assess ICF, eligibility, AE, device accountability, and primary endpoint data as further defined in the Monitoring Plan. Sponsor management will be provided copies of monitoring reports within 10 days of the visit.

An Independent clinical audit may be conducted by Sponsor to ensure that monitor is following the CMP.

10.1.7 QUALITY ASSURANCE AND QUALITY CONTROL

The clinical site will perform internal quality management of study conduct, data and biological specimen collection, documentation and completion.

Quality control (QC) procedures will be implemented beginning with the data entry system and data QC checks that will be run on the database will be generated. Any missing data or data anomalies will be communicated to the site(s) for clarification/resolution.

Following written Standard Operating Procedures (SOPs), the monitors will verify that the clinical trial is conducted and data are generated and biological specimens are collected, documented (recorded), and reported in compliance with the protocol, International Conference on Harmonization Good Clinical Practice (ICH GCP), and applicable regulatory requirements.

The investigational site will provide direct access to all trial related sites, source data/documents, and reports for the purpose of monitoring and auditing by the sponsor, and inspection by local and regulatory authorities.

10.1.8 DATA HANDLING AND RECORD KEEPING

10.1.8.1 DATA COLLECTION AND MANAGEMENT RESPONSIBILITIES

Data collection is the responsibility of the clinical trial staff at the site under the supervision of the site investigator. The investigator is responsible for ensuring the accuracy, completeness, legibility, and timeliness of the data reported.

All source documents should be completed in a neat, legible manner to ensure accurate interpretation of data.

Hardcopies of the study visit worksheets will be provided for use as source document worksheets for recording data for each participant enrolled in the study. Data recorded in the electronic case report form (eCRF) derived from source documents should be consistent with the data recorded on the source documents.

Clinical data (including adverse events (AEs), concomitant medications, and expected adverse reactions data) and clinical laboratory data will be entered into EDC, a 21 CFR Part 11-compliant data capture system provided by the EDC Vendor. The data system includes password protection and internal quality checks, such as automatic range checks, to identify data that appear inconsistent, incomplete, or inaccurate. Clinical data will be entered directly from the source documents.

10.1.8.2 STUDY RECORDS RETENTION

The investigator(s) will retain all study records for a minimum of 15 years from the date of Federal Financial Report submission. No records will be destroyed without the written consent of the sponsor (Capillary Biomedical, Inc.). The sponsor will inform the investigator(s) when the study records are no longer need to be retained.

10.1.9 PROTOCOL DEVIATIONS

A protocol deviation is any noncompliance with the clinical trial protocol, International Conference on Harmonization Good Clinical Practice (ICH GCP), or Manual of Procedures (MOP) requirements. The noncompliance may be either on the part of the participant, the investigator, or the study site staff. As a result of deviations, corrective actions are to be developed by the site and implemented promptly.

These practices are consistent with ICH GCP:

- 4.5 Compliance with Protocol, sections 4.5.1, 4.5.2, and 4.5.3
- 5.1 Quality Assurance and Quality Control, section 5.1.1
- 5.20 Noncompliance, sections 5.20.1, and 5.20.2.

All deviations must be addressed in study source documents, reported to the sponsor. The site investigator is responsible for knowing and adhering to the reviewing IRB requirements. Further details

about the handling of protocol deviations will be included in the MOP. Deviations involving risk to participants will be reported to the IRB and the sponsor within 10 working days.

10.1.10 PUBLICATION AND DATA SHARING POLICY

The clinical trial investigators will determine the authorship of peer publications based upon the work effort performed. Data and samples/specimen are owned by the university and shared with the Sponsor.

10.1.11 CONFLICT OF INTEREST POLICY

The independence of this study from any actual or perceived influence, such as by the medical device industry, is critical. Therefore, any actual conflict of interest of persons who have a role in the design, conduct, analysis, publication, or any aspect of this trial will be disclosed and managed. Furthermore, persons who have a perceived conflict of interest will be required to have such conflicts managed in a way that is appropriate to their participation in the design and conduct of this trial. The study leadership in conjunction with the National Institutes of Health- NIDDK has established policies and procedures for all study group members to disclose all conflicts of interest and will establish a mechanism for the management of all reported dualities of interest. All investigators will disclose all actual and perceived conflicts of interest to the Conflicts of Interest Committee and establish/implement a plan to manage the conflict.

10.2 ABBREVIATIONS

AE	Adverse Event
ANCOVA	Analysis of Covariance
BG	Blood Glucose
CBC	Complete Blood Count
CFR	Code of Federal Regulations
CGM	Continuous Glucose Monitor
CLIA	Clinical Laboratory Improvement Amendments
CMP	Clinical Monitoring Plan
COC	Certificate of Confidentiality
CONSORT	Consolidated Standards of Reporting Trials
CRF	Case Report Form
CRU	Clinical Research Unit
CSII	Continuous Subcutaneous Insulin Infusion
DCC	Data Coordinating Center
DHHS	Department of Health and Human Services
DRE	Disease-Related Event
DSMB	Data Safety Monitoring Board
EC	Ethics Committee
ECG	Electrocardiogram

eCRF	Electronic Case Report Forms
FDA	Food and Drug Administration
FDAAA	Food and Drug Administration Amendments Act of 2007
FFR	Federal Financial Report
GCP	Good Clinical Practice
GLP	Good Laboratory Practices
GMP	Good Manufacturing Practices
GWAS	Genome-Wide Association Studies
HIPAA	Health Insurance Portability and Accountability Act
IB	Investigator's Brochure
ICH	International Conference on Harmonisation
ICMJE	International Committee of Medical Journal Editors
IDE	Investigational Device Exemption
IND	Investigational New Drug Application
IRB	Institutional Review Board
ISM	Independent Safety Monitor
ISO	International Organization for Standardization
ITT	Intention-To-Treat
IV	Intravenous
LSMEANS	Least-squares Means
MedDRA	Medical Dictionary for Regulatory Activities
MOP	Manual of Procedures
MSDS	Material Safety Data Sheet
NCT	National Clinical Trial
NIH	National Institutes of Health
NIH IC	NIH Institute or Center
OHRP	Office for Human Research Protections
PI	Principal Investigator
QA	Quality Assurance
QC	Quality Control
SAE	Serious Adverse Event
SAP	Statistical Analysis Plan
SC	Subcutaneous(ly)
SMBG	Self-monitored Blood Glucose
SMC	Safety Monitoring Committee
SOA	Schedule of Activities
SOC	System Organ Class
SOP	Standard Operating Procedure
UP	Unanticipated Problem
US	United States
VAS	Visual Analogue Scale

10.3 PROTOCOL AMENDMENT HISTORY

The table below is intended to capture changes of IRB-approved versions of the protocol, including a description of the change and rationale. A Summary of Changes table for the current amendment is located in the Protocol Title Page.

Version	Date	Description of Change	Brief Rationale
A	2/12/2020	Initial release	As submitted to FDA
B	3/19/2020	Respond to FDA requests	IDE G190079-S001 approved
C	4/16/2020	Clarify clamp procedures, extend screening time duration and allow Dexcom G6 run-in period	Support recruitment at Study Center during COVID-19
D	7/20/2020	Revised blood sampling schedule and clarified other procedures; specified independent safety monitor	Align to Study Center procedure
E	10/15/2020	Increased basal stabilization period from maximum of 3.0 to 3.5 hours and revised glucose infusion "trigger" value during euglycemic clamp from 90 mg/dL to be a value 5 mg/dL less than the mean of the three values obtained during Baseline Period II	These changes improve the likelihood of achieving a stable baseline prior to initiating the clamp procedure and also reduce the risk of hypoglycemic overshoot in the early phase of the clamp procedure
F	11/24/2020	Clarify procedure; added one time rescreen for A1C and C-peptide	Align to Study Center procedure; Capillary Biomedical's standard procedure has been to allow for a single rescreen attempt for key labs (e.g. A1C and c-peptide).

1 OVERVIEW

1.1 INTRODUCTION

This documentation describes the planned data analyses for the CapBio 150-1022 Clinical Study.

2 OBJECTIVES

2.1 Primary Objective

The primary objective of this study is to assess the reliability of insulin delivery using the investigational Achilles infusion set by evaluating the rate of decline of the glucose lowering effect of insulin from DOI through day 7 (0, 3, 5, and 7 days post insertion) compared to the commercially available control infusion set.

2.2 Secondary Objectives

Secondary objectives include:

- To assess other pharmacodynamics (PD) parameters of insulin within and across treatments following subcutaneous delivery using Achilles vs Teflon control set on DOI (day 0) and days 3, 5, and 7 post insertion
- To assess pharmacokinetic (PK) parameters within and across treatments following subcutaneous insulin delivery using Achilles vs Teflon control set on DOI and days 3, 5 and 7 post insertion.
- To assess continuous glucose monitoring (CGM) data, comparing data within and across treatments.
- To assess performance of the investigational infusion set on DOI (day 0) through day +7 (8th calendar day of wear) for each treatment

2.3 Safety Objectives

- To assess safety and tolerability of the investigational infusion set on DOI through day +7 post insertion (8th calendar day of wear) for each treatment as measured by infusion set failure.

2.4 Analysis Software

SAS 9.4 (or later) Windows.

2.5 MODIFICATIONS FROM THE STATISTICAL SECTION IN THE PROTOCOL

After the 7th subject completed the study, sponsor decided to terminate the study.
Thus :

- The analyses carries out using all available data will be considered as final analyses. No intrime analyses will be carried out.
- All analyses defined in this SAP will be done. However, it is expected some of them may not have results/outputs generated due to the small sample size.

3 INVESTIGATIONAL PLAN

[figure not shown]
3.1 STUDY DESIGN AND RANDOMIZATION

3.2 Study Design

This is an open, single-center, 2-way randomized, cross-over trial investigating the survivability, consistency, efficacy, and safety of an extended wear time investigational insulin infusion set (CapBio Achilles). This is achieved by measuring PK and PD profiles of a bolus of rapid acting insulin on 4 separate days of CSII set wear time during 2 separate wear periods in up to 30 adult patients with T1DM.

3.3 Randomization

Participants will be randomized at Visit 1 1:1 to either undergo glucose clamp testing with the Achilles investigational cannula or commercially available control CSII set. If participant is randomized into the Achilles infusion set treatment group during Treatment Period 1, they will undergo Treatment Period 2 with the Teflon control set and vice versa. This allows the participant to act as his/her own control and minimizes user bias.

3.3.1 Study Visit Window

Study visit windows have has been defined for each visit as in the table below where day 0 is the day of the first set insertion (DOI).

Visit	Visit Window
Screening/Baseline	-28 to -1 days
Wear Period	DOI to +7 days inclusive in each treatment period
Study Completion	8 th calendar day or upon infusion set failure in each treatment Period
Follow-up	Patients will receive follow-up phone call by staff 1 day after each period

3.4 SAMPLE SIZE JUSTIFICATION

A sample size of 24 participants is sufficient to generate 90% power for a 2-tailed $p=0.05$ comparison of the $\ln(\text{AUC}_{0-300(\text{GIR})})$ slope contrasts (=control minus Achilles), within this 2x2 crossover design. In addition to the usual regularity assumptions for the 2x2 crossover design (i.e. no carryover effects), this computation was based on the following assumptions:

1. The $\ln(\text{AUC}_{0-300(\text{GIR})})$ values are normally distributed.
2. The within participant variance is 40% of the total variance.
3. The study day correlation matrix of the within-participant $\ln(\text{AUC}_{0-300(\text{GIR})})$ assessments is AR (autoregressive model) with correlation $r=0.5$.
4. The within plus among participant variance for the $\ln(\text{AUC}_{0-300(\text{GIR})})$ values is 0.21 (based on previous studies).
5. The difference in slopes (Achilles minus control) is at least 0.07.

4 STATISTICAL AND ANALYTICAL PROCEDURES

4.1 ANALYSIS POPULATIONS

4.1.1 Safety Population

The safety population includes all patients who had either an investigational or control cannula implanted.

4.1.2 Intent-to-Treat (ITT) Population

The intent-to treat (ITT) population includes all patients that meet all inclusion criteria and none of the exclusion criteria and are randomized to treatment sequence and complete at least one glucose clamp procedure will be included in the ITT population.

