Commercial subcutaneous insulin infusion sets have a known failure rate of approximately 15 - 25% prior to their labelled 3 day (72 hour) wear duration. Therefore, T1DM patients are accustomed to frequent change outs with commercial infusion sets. In response to these known issues, the Capillary Biomedical Achilles infusion set incorporates a kink-resistant coil-reinforced soft polymer cannula. This cannula contains one distal and three proximal holes to ensure redundancy and extended wear-time of up to 7 days.

Failure of the investigational Achilles infusion set may occur during the 7 day extended wear period. However, if Achilles infusion set failure occurs at any time during the home wear period, the participant will simply be instructed to change out the investigational device for their standard commercially available set to maintain CSII therapy. This is the same risk associated with a use of commercially available infusion sets.

CSII set infusion site irritation and infection are familiar risks to insulin pump users. The investigational Achilles infusion set will be manually inserted and secured (taped) to an appropriately selected body location by a trained study staff member. Participants will be observed at the study center for 3 hours to ensure initial Achilles infusion set function prior to clinic discharge and start of home-use period. Study staff may attempt infusion set insertion three times. If insertion is not successful after 3 attempts, the Achilles infusion set is considered failed for this study participant.

Study participants will be instructed to check the infusion site for any skin abnormalities on a daily basis. All findings of skin irritation/infection (including tape reactions or cannula dislodgement) will be carefully monitored and recorded in a participant diary. If there is evidence of an infection at the infusion site, participants will be instructed to remove the infusion set and insert a fresh insulin infusion set as per their clinical routine. The Achilles infusion set will be placed in a provided container and biohazard bag. Participants are instructed to photograph the inflamed infusion site and contact the study staff via the provided study hotline.

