9.3 POPULATIONS FOR ANALYSES

Intention-to-Treat (ITT) Analysis Population: all patients that meet all inclusion criteria and none of the exclusion criteria and are randomized to treatment sequence and complete at least one glucose clamp procedure will be included in the ITT population.

Safety Analysis Population: all patients who had either an investigational or control cannula implanted.

Per-Protocol (PP) Analysis Population: all patients who completed both treatment sequences with no major protocol violations.

The primary effectiveness analysis will be based on the ITT participant population. Sensitivity analyses of the primary effectiveness endpoint will be generated based on the PP population. The ITT population may contain some patients that complete the first treatment, but not the second, and vice versa. This will require the use of imputation methods for missing values, which are documented in Section 9.4.2.

The primary safety analysis will be based on the Safety population. All secondary and exploratory effectiveness analyses will use the PP population.

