9.4.3 ANALYSIS OF THE SECONDARY ENDPOINT(S)

Secondary analyses will use the both ITT and PP populations for analysis.

The survival of the Achilles and control infusion sets will be compared using a discrete lifetable analysis over study days 0, 3, 5, and 7 and the discrete form of the log-rank test.

All pharmacokinetic parameters (AUCs , t_{50} , C_{max} , t_{max} , MRT for the insulin concentration by time curve, etc.) will be estimated using non-compartmental models and log-transformed before analysis. Means for the two treatment groups will be compared in a mixed-effects (repeated-measures) linear model with treatment and period as fixed effects and participant as a random effect. The mean difference between treatments (on the log-scale) will be compared with a two-sided test using significance level $\alpha=0.05$. Then mean ratio and its 95% confidence interval will be calculated by inverse-transforming the mean difference and its 95% confidence interval.

All pharmacodynamic parameters (AUCs , onset time and time to return to baseline for the glucose concentration by time curve, etc.) will be estimated using non-compartmental models. Means for the two treatment groups will be compared in a mixed-effects (repeated-measures) linear model with treatment and period as fixed effects and participant as a random effect. The mean difference between treatments will be compared with a two-sided test using significance level $\alpha=0.05$. Wilcoxon signed rank tests will be used if the data is significantly skewed.

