4.1.4 Populations Used for Analyses

The primary effectiveness analysis will be based on the ITT population. Sensitivity analyses of the primary effectiveness endpoint will be generated based on the PP population.

The demographics and baseline characteristics will be based on ITT Population.

The safety analysis will be based on the Safety population.

All secondary effectiveness analyses will use ITT population , with sensitivity analyses using the PP population (similar to the primary effectiveness analysis).

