4.3.2.7 Performance of the Investigational Infusion Set

4.3.2.7.1 Daily Insulin Infusion Set Survival Rate

Infusion set failure is defined as an episode of unexplained hyperglycemia that did not respond to a correction bolus, hyperglycemia associated with elevated serum ketone measurement in the absence of evidence of intercurrent illness, evidence of infusion site infection, or non-resolvable insulin infusion pump occlusion alarm. These conditions indicate failure of the system at the level of the subcutaneously indwelling infusion cannula.

Infusion sets can also fail to provide insulin as a result of other system performance issues, such as failure of the insertion attempt to pierce the skin, accidental removal of the set by inadvertent application of tension to the tubing (e.g. “tubing caught on a doorknob”), or failure of the adhesive to secure the cannula housing to the skin for the full duration of study.

The daily infusion set survival rate is calculated by the # of non-fail infusion sets on that day divided by the total # of infusion sets inserted. Survival curves will be generated for both “infusion set failure” episodes and all failures combined (“infusion set failure” combined with “other system performance issues” as defined above).

The day will be normalized to the day of the insertion where first day is set to Day 0.

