4.4.4.2 Analyses of Secondary Endpoints

4.4.4.2.1 Daily Insulin Infusion Set Survival Rate

The survival of the Achilles and control infusion sets will be compared using a discrete lifetable analysis over study days 0, 3, 5, and 7 and the discrete form of the log-rank test.

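### The SAP's ITT set requires a completed clamp, so a Day 0 set failure can remove a participant from the set-survival analysis; the expected number is small

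*SAP*

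**What the plan says.** **Population.** SAP 4.1.2 admits to ITT those who "meet all inclusion criteria and none of the exclusion criteria and are randomized to treatment sequence" and who "complete at least one glucose clamp procedure will be included in the ITT population". Protocol 9.3 sets the same conditions.

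**Assignment.** SAP 4.1.4 states: "All secondary effectiveness analyses will use ITT population", with PP as sensitivity. Set survival is one of these analyses. SAP 4.4.4.2.1 says "The survival of the Achilles and control infusion sets will be compared using a discrete lifetable analysis" and, unlike the sections that follow it, names no population, so 4.1.4 governs. SAP 4.4.4.1, which calls the set failure rate the primary endpoint, also uses ITT with PP as sensitivity. The protocol is not consistent with itself here. Section 9.3 says "All secondary and exploratory effectiveness analyses will use the PP population", and 9.4.3 says "Secondary analyses will use the both ITT and PP populations for analysis".

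**What counts as failure.** SAP 4.3.2.7.1 lists "failure of the insertion attempt to pierce the skin" among the other system performance issues, which enter only the curve for all failures combined. Protocol 2.3.3 adds: "If insertion is not successful after 3 attempts, the Achilles infusion set is considered failed for this study participant". The daily survival rate in SAP 4.3.2.7.1 divides by the number of all sets inserted and mentions no clamp.

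**The concern.** The clamp condition is settled after randomization, and set failure can determine whether it is met. The documents give these ways for a failure to leave no completed Day 0 clamp:

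- The set cannot be inserted (Protocol 2.3.3; SAP 4.3.2.7.1).
- The clamp is stopped for persistent hyperglycemia, and the set is judged failed if a correction bolus does not work (Protocol 6.1.1.5).
- The failed cannula has already been removed, in which case no clamp is done (Protocol 1.3, footnote 6).

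A change-out during a clamp visit ends that treatment phase (Protocol 6.1.1.8), so no later clamp in the same period can make up for it. If period 2 yields no completed clamp either, the participant is outside ITT, and any set failure goes uncounted in the failure and survival analyses.

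This matters for an endpoint whose purpose is to count failures, because the participants removed are removed for having failed. PP asks for both treatment sequences to be completed, so the planned sensitivity analysis cannot be relied on to bring them back.

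**Working it through.** The plan gives no figure for this loss, so there is none to reproduce. The check sizes it.

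**Inputs**
- Day 0 failure probability: 15%, the initial Teflon failure rate in the 7-day wear study cited in Protocol 2.2.3. Applying it to both arms is an assumption.
- w, the probability of not returning for period 2 after a period 1 failure: not given. Assumed 0 and 20%, with 100% as the extreme.
- The two failures within a participant: assumed independent, then perfectly correlated as the extreme.
- Number of participants: 7, because the trial was stopped after the seventh completer (SAP 2.5). The number randomized is not stated, so 7 only sets the scale.
- A clamp stopped early is taken as not completed; neither document defines completion.

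**Probability of leaving ITT through early failure**

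With the two sequences equally likely, and pA and pC the Day 0 failure probabilities for Achilles and control:

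P = ½ × {pA × [w + (1 − w) × pC] + pC × [w + (1 − w) × pA]}

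| Assumptions | P | Expected of 7 | Chance of at least one in 7 |
|---|---|---|---|
| 15% both, all return | 0.15 × 0.15 = 0.0225 | 0.16 | 1 − 0.9775^7 = 15% |
| 15% both, 20% do not return | 0.15 × (0.20 + 0.80 × 0.15) = 0.048 | 0.34 | 1 − 0.952^7 = 29% |
| Achilles 0%, control 15%, all return | 0 | 0 | 0 |
| Achilles 0%, control 15%, 20% do not return | ½ × 0.15 × 0.20 = 0.015 | 0.10 | 10% |
| Upper bound: nobody returns, or perfect correlation, at 15% both | 0.15 | 1.05 | not computed |

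**Effect on the Day 0 failure rate shown (true rate 15%)**
- All return: 2 sets and 0.30 failures per participant. Excluded: 2 × 0.0225 = 0.045 sets, all failed. ITT rate = (0.30 − 0.045)/(2 − 0.045) = 13.0%.
- 20% do not return: sets = 1 + 0.85 + 0.15 × 0.80 = 1.97; failures = 0.15 × 1.97 = 0.2955. Excluded: 0.15 × 0.20 + 2 × 0.15 × 0.80 × 0.15 = 0.066. ITT rate = 0.2295/1.904 = 12.1%.
- Nobody returns: sets = 1.85; failures = 0.2775; excluded = 0.15. ITT rate = 0.1275/1.70 = 7.5%.
- Perfect correlation: every Day 0 failure is excluded, so the ITT rate is 0%.

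**One hypothetical exclusion.** An arm with 2 failures in 7 (survival 71.4%) would become 1 in 6 (survival 83.3%), a change of about 12 points.

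**The case against.** The case against has several parts.

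- **The route is narrow.** One completed clamp in either period is enough, and a participant who fails in period 1 is asked back for period 2 (Protocol 6.1.1.8). Someone who completes a clamp there stays in ITT with the period 1 failure counted. This stands, and it is why the expected loss is a fraction of one participant.
- **15% is probably too high.** It comes from a different Teflon set, where it reflected kinking. Protocol 2.3.3 expects much lower early failure with the Silhouette control and cites no kinking for Achilles in pre-clinical work. This also stands. In the other direction, the same cited study found that wear length depended mainly on the individual, which suggests failures cluster within participants and moves the figure towards the upper bound.
- **Failures are visible elsewhere.** Device malfunctions are reported on the Safety population (SAP 4.4.5.4). This stands in part. Those tables are descriptive, and the list in SAP 4.3.3.1 has no item for occlusion alarms. The Safety population requires a cannula to have been implanted (SAP 4.1.1), so a failed insertion may be missing there too.
- **The denominator may already mean every set.** SAP 4.3.2.7.1 can be read that way. If so, it conflicts with 4.1.4, and the SAP still has to say which governs.

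A reader might also infer that the eligibility condition makes exclusion depend on the outcome. The documents do not support that. Eligibility is screened at Visit 0, before randomization at Visit 1. Ineligibility may come to light later (Protocol 7.2), but the entry criteria do not turn on how the study set performs. The condition is a separate, minor departure from ITT.

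**Conclusion.** The point holds in limited form. A stated rule can remove early failures from the analysis meant to count them, and it is not reconciled with the SAP's own denominator. Where it operates, absolute set survival is overstated.

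At an assumed 15% Day 0 failure in both arms with independent failures, the expected loss is 0.16 to 0.34 of 7 participants. The upper bound is about 1 of 7, and the loss is smaller if the protocol's expectation for the Silhouette is right.

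Two stronger conclusions may tempt a reader. One is that the reported failure rate is off by some 12 points. That would need an excluded early failure, and the documents report none. The other is that the comparison is tilted towards Achilles. If both sets fail early, each arm loses a failure. If the participant leaves after period 1, only that arm loses one. With Achilles at 0% and control at 15%, any loss would flatter the control, so the direction is not fixed.

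The slope analysis is essentially unaffected, since a participant without an AUC contributes nothing to it.

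**What to change.** - Analyse set failure and survival (SAP 4.4.4.1 and 4.4.4.2.1) on all randomized participants with a study-set insertion attempted, with no clamp condition, and name this population in both sections.
- Count a failed insertion as a Day 0 event in the curve for all failures combined.
- Align the denominator in SAP 4.3.2.7.1 with this population, so that attempted insertions are included.
- Keep the present set for the AUC slope model, labelled modified ITT, and leave eligibility exclusions to PP.

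The cost is a few sentences in the SAP and one rerun of the survival tables. No new data are needed, provided failed insertion attempts were recorded. The Safety population is not a full substitute, because it requires an implanted cannula.
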